2.3 Protocol of intervention

To assess status of oral health, inspection and orthopantomography have carried out; if decay or periodontitis were suspected, an endoral radiograph was performed in order to confirm poor prognosis before extraction. Only when indicated (i.e., teeth near to inferior alveolar nerve and paranasal sinuses), a cone beam computed tomography (CBCT) of the maxillofacial region was performed. Extractions were performed by a resident in oral surgery.

Starting from the day before extraction, oral antibiotics (amoxicillin-clavulanate 1g and metronidazole 500mg, three times daily; in case of penicillin allergy, erythromycin 600mg, three times daily), and local antiseptics (0.2% chlorhexidine mouthwash) for a period of 7 days were prescribed (Table 3).

Written informed consents about off-label use of metronidazole (needed in Italy), oral surgery protocol and MRONJ risk were obtained from patients.

Table 3. Descriptive of profilaxis protocols to prevent MRONJ

	Group T	Group C
Prophylaxis	Amoxicillin-clavulanate 1g + Metronidazole 500 mg three times daily (in case of penicillin allergy: Erythromycin 600mg + Metronidazole 500 mg three times daily)	Amoxicillin-clavulanate 1g + Metronidazole 500 mg three times daily (in case of penicillin allergy: Erythromycin 600mg + Metronidazole 500 mg three times daily)
Adjuvant Therapy	Injections of a 15 mL mixture of Oxygen-Ozone (O_2O_3) with a 26Gx 1/2 - 0.45x13 mm needle	NA

GROUP T

On the day of the surgery (T0), the surgical protocol involved superficial local anesthesia by EMLA® cream, loco-regional anesthesia, incision and flap debridement, extraction of the tooth with poor prognosis, osteoplasty, intra-tissutal perialveolar injections of a 15-mL mixture of OxigenOzone (O_2O_3) with a 26Gx 1/2 - 0.45x13 mm needle and insufflation of the same mixture in the post-extraction site for at least 1 minute, hemostasis, and suture.

Additionally, each patient was scheduled for supplementary visits during which the OxigenOzone mixture was applied at T1 (3-5 days), T2 (14 days) and T3 (6 weeks) after the extraction.

When possible, depending on the patient's compliance and willingness, in 9 patients the mixture was applied twice a week within T2, until complete clinical healing or in case of ONJ sequestration formation.

GROUP C

On the day of the surgery (T0), the surgical protocol for Group B included the following steps: superficial local anesthesia using EMLA® cream, loco-regional anesthesia, incision and flap debridement, extraction of teeth with a poor prognosis, osteoplasty, achieving hemostasis, and suture.

Healing Evaluation and follow-up

In both groups, patients underwent additional follow-up visits at T1 (3-5 days), T2 (14 days), and T3 (6 weeks) post-extraction to meticulously monitor surgical wound healing by Inflammatory Proliferative Remodeling (IPR) Wound Healing Scale (Table 4) [20], and to record pain intensity by the NRS scale for enhanced ease of use, rather than the originally planned VAS scale [22].

The IPR scale provided a comprehensive assessment of wound healing through distinct subscales, each ranging from 0 to 1, resulting in a total score ranging from 0 to 16. These subscales evaluated the inflammatory response, proliferative response, and remodeling process. At the end of the follow-up period, the total IPR score was computed, with scores spanning from 0 to 16. Scores of 0-4 denoted poor healings, scores of 5-10 indicated acceptable healing, while scores of 11-16 suggested excellent healing.

Table 4. IPR (Inflammatory Proliferative Remodeling) Scale [21]

T/PHASE	Parameter	Score 0	Score 1	Total score
INFLAMMATORY T: 3-5 DAYS	Bleeding, spontaneously or on palpation	Yes	No	/8
	Granulation tissue	Yes	No	
	Haematoma	Yes	No	
	Tissue colour	Redder or whiter than opposite side tissue	Like the opposite side tissue	
	Incision margins	Incomplete flap closure/fibrin clot/partial necrosis/complete necrosis	Complete flap closure/fine fibrin line	

	Suppuration Edema NRS (1–10) Pain NRS (1–10)	Yes NRS 6–10 NRS 6–10	No NRS 1–5 NRS 1–5	
PROLIFERATIVE T: 14 DAYS	Re-epithelialisation	Partial	Complete	/5
	Tissue colour	Redder or whiter than opposite side tissue	Like the opposite side tissue	
	Scar	Scar wider than 2 mm/contour irregularity	No scar/scar less wide than 2 mm/contour regularity	
	Suppuration Pain NRS (1–10)	Yes NRS 6–10	No NRS 1–5	
REMODELING T: 6 WEEKS	Scar	Scar wider than 2 mm/contour irregularity	No scar/scar less wide than 2 mm/contour regularity	/3
	Tissue colour	Redder or whiter than opposite side tissue	Like the opposite side tissue	
	Pain NRS (1–10)	NRS 6–10	NRS 1–5	
TOTAL PROCESS				/16

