01/09/2023

[NCT ID not yet assigned] Unique Protocol ID: OZONE_EXO

OZONE_EXO: Comparative Analysis of Protocols for Dental Exactions in Patients at Risk of MRONJ: Case-control Study

Study Protocol

This study, entitled the OZOPROMAF protocol, was reviewed and approved by the Ethics Committee of University Hospital of Palermo, Policlinico P. Giaccone (approval number 01/2018).

Patients were consecutively enrolled from February 2018 to March 2020.

The study protocol conformed with the ethical guidelines of the 1964 Declaration of Helsinki and its later amendments or comparable ethical standards. All participants gave their written informed consent.

The aim of this study was to carry out a case-control study in order to compare two different protocols of dental extractions in patients at risk of MRONJ, with and without infiltration of a mixture of oxygen-ozone.

According to the considered criteria of inclusion and exclusion (Table 1), this study recruited 117 patients, 27 male and 90 female. Out of these patients, 54 had osteometabolic conditions, 57 were cancer patients, and 6 had both osteometabolic disease and cancer.

Table 1. Inclusion and exclusion criteria.

Inclusion criteria	
· age \geq 18 yrs· patients at risk of developing MRONJ for previous or current administration of drugs related· poor prognosis (for caries and/or periodontitis) of one or more teeth suitable for dental extraction
Exclusion criteria	
· previous radiation in the head and neck area· neoplastic involvement of the jaw· previous MRONJ diagnosis

The patients were randomly assigned to two groups using a simple randomization method. Specifically, a software program was used to arbitrarily select 38 patients (group Test) to receive ozone therapy by insufflation to the post-extraction site. The remaining 79 patients (group Control) did not receive this treatment.

During first consultation, medical, pharmacological, and dental history of patients were recorded, including age, sex, indications for use of MRONJ-related drugs, type and duration of MRONJ-related medication use, medical history of chemotherapy, concurrent use of other medications, other concomitant diseases, and smoking habits.

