The patients recruited for the study (Table 2) were: "*onc1*" (cancer patients undergoing antiresorptive and/or anti-angiogenic therapies for medical indications), "*onc2*" (cancer patients taking antiresorptive treatments to manage osteometabolic disorders), and "*ost*" (non-oncologic patients taking antiresorptives for the treatment of osteometabolic conditions). So, based on type of drugs, route of administration and cumulative dose two risk categories were identified, namely low and high risk: *onc1* patients were generally considered to be at high risk; *onc2* and *ost* patients belonged to low-risk category.

Table 2. Descriptive data of enrolled patients.

	Test (N=38)	Controls (N=79)
Age		
Mean (SD)	66.7 (12.1)	69.6 (9.82)
Median [Q1, Q3]	71.00 [56.00, 74.75]	70.00 [63.00, 77.00]
Sex		
F	27 (71.1%)	63 (79.7%)
M	11 (28.9%)	16 (20.3%)
Patient risk category		
high	22 (57.9%)	35 (44.3%)
low	16 (42.1%)	44 (55.7%)
Patient type		
onc1	22 (57.9%)	35 (44.3%)
onc2	4 (10.5%)	2 (2.5%)
ost	12 (31.6%)	42 (53.2%)
Type of therapy		
antiresorptive medications	31 (81.6%)	74 (93.7%)
anti-angiogenetic medications	2 (5.3%)	1 (1.3%)
both	5 (13.2%)	4 (5.1%)

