2.4 Statistical methods

The statistical analysis was performed using the R Statistical Software (v4.1.2; R Core Team 2021). Categorical variables were expressed as counts and percentages, quantitative variables as mean (standard deviation) or as median and interquartile range (the 25th and 75th percentiles), in case of skewed distributions. The Chi-square or the Fisher's exact test was used to compare groups A and B for categorical variables. Student's t test or the Wilcoxon-Mann-Whitney test was calculated to compare groups A and B for continuous variables. Statistically significant differences were assessed using two-sided P-values below 0.05.

At multivariable analysis, logistic regression was used to model binary responses (IPR>Median vs IPR≤Median) as related to demographic, pharmacological, systemic, and clinical covariates that have resulted significant at univariable analysis.

Table 4. IPR comparative statistical analysis

	Group T (ozone therapy) (N=38)	Group C (controls) (N=79)	P-value
Inflammatory T1 (3–5 Days)[§]			
Mean (SD)	2.00 (0.870)	2.49 (0.875)	0,006
Median [Q1, Q3]	2.00 [1.00, 2.75]	2.00 [2.00, 3.00]	
Proliferative T2 (14 Days)[§]			
Mean (SD)	4.24 (1.51)	3.70 (1.02)	<0.001
Median [Q1, Q3]	5.00 [4.00, 5.00]	4.00 [3.00, 4.00]	
Remodelling T3 (6 Weeks)[§]			
Mean (SD)	3.00 (0)	2.96 (0.192)	0,230
Median [Q1, Q3]	3.00 [3.00, 3.00]	3.00 [3.00, 3.00]	
IPR_Total Process[§]			
Mean (SD)	9.37 (1.79)	9.15 (1.38)	0,275
Median [Q1, Q3]	9.50 [9.00, 10.00]	9.00 [8.00, 10.00]	

[§]Wilcoxon signed-rang test

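### Number of teeth and reason for extraction are neither shown by arm nor fixed as covariates, so an imbalance in extent of surgery cannot be seen and is not reliably removed

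*Combined protocol and SAP*

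**What the plan says.** Table 1 admits patients with "poor prognosis (for caries and/or periodontitis) of one or more teeth suitable for dental extraction". On allocation, the text below Table 1 says: "The patients were randomly assigned to two groups using a simple randomization method". The result is 38 ozone patients (Group T) and 79 controls (Group C).

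Section 2.3 describes the surgery for Group T as "extraction of the tooth with poor prognosis, osteoplasty", followed by ozone, hemostasis and suture. For Group C it reads "extraction of teeth with a poor prognosis, osteoplasty, achieving hemostasis, and suture". Ozone aside, the listed steps match.

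At the first consultation, "medical, pharmacological, and dental history of patients were recorded, including age, sex, indications for use of MRONJ-related drugs". The list goes on to drug type and duration, chemotherapy, other medication, other diseases and smoking. It is introduced as examples, so it is not exhaustive, but it does not name number of teeth or reason for extraction. The baseline table ("Table 2. Descriptive data of enrolled patients") has rows for age, sex, risk category, patient type and type of therapy only.

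Section 2.4 plans the group comparisons as follows: "Student's t test or the Wilcoxon-Mann-Whitney test was calculated to compare groups A and B for continuous variables". Its multivariable analysis is a logistic model of IPR above versus at or below the median. The covariates come from broad classes, clinical ones among them, and enter if significant univariably. The IPR results table gives four unadjusted comparisons.

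**The concern.** Each patient contributes one IPR score. Many of its items describe the wound: flap closure, suppuration, re-epithelialisation, scar width. Section 2.3 does not say which socket is scored when several are operated on. If a failing sign at any site counts, the score falls as the number of sockets rises, whatever the treatment. An infected periodontal site may also heal differently from a carious one.

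These two variables describe the operation itself, and they are the ones a reader would want to see balanced. They are not reported by arm. The phase scores are compared without adjustment. The logistic model answers a different question, on a dichotomised outcome, and admits a clinical covariate only if it happens to pass a significance screen. A prognostic factor that is moderately unbalanced and not individually significant would be left out.

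At stake is the size and precision of the day-14 (T2) difference, the only statistically significant row that favours ozone. The T3 and total rows favour ozone numerically but are not significant.

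**Working it through.** **Inputs from the IPR results table.** T2: ozone 4.24 (SD 1.51, n = 38), control 3.70 (SD 1.02, n = 79), P < 0.001. T1: ozone 2.00, control 2.49. From Table 4 of section 2.3: T1 has 8 items and T2 has 5, each scored 0 or 1, higher being better.

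**Step 1: reproduce the printed T2 result.** The difference is 4.24 − 3.70 = 0.54. All integer score distributions compatible with the printed n, mean, SD and quartiles were enumerated (4 for ozone, 102 for control). The two-sample rank-sum test gives P between 0.000003 and 0.00015 over all pairs, so P < 0.001 reproduces. From the summary statistics, the pooled t test gives P = 0.024 and Welch's gives 0.051.

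**Step 2: how large a chance imbalance could be.** Assume half of all patients have two extractions (not in the documents). Under random allocation the 95% range for the difference in that share is 1.96 × √(0.25 × (1/38 + 1/79)) = 0.193, about ±19 percentage points.

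**Step 3: what that imbalance is worth at T2.** Assume that a failing sign at any site scores 0 and that pass rates are equal across sites (not in the documents). The control pass rate per item is 3.70/5 = 0.74. Let π be the single-site pass rate and ρ the within-patient correlation. With half the patients at two sites:
- ρ = 0: 0.5π + 0.5π² = 0.74 gives π = 0.815. A second site costs 5 × 0.815 × 0.185 = 0.75 points. The shift is 0.193 × 0.75 = 0.15.
- ρ = 0.5: 0.75π + 0.25π² = 0.74 gives π = 0.783. The cost is 5 × 0.5 × 0.783 × 0.217 = 0.43 points. The shift is 0.193 × 0.43 = 0.08.
- ρ = 1: a second site costs nothing, and the shift is 0.

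As a cross-check, simply assume that a multi-tooth extraction costs 0.5, 1.0 or 1.5 points. The same imbalance then shifts T2 by 0.10, 0.19 or 0.29. Explaining all of 0.54 would need an imbalance of 0.54/0.5 = 108 (impossible), 0.54/1.0 = 54 or 0.54/1.5 = 36 percentage points.

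**Step 4: test the literal reading of the surgical wording.** Suppose every control had two sites, every ozone patient had one, and ozone had no effect. Solve π² + ρπ(1 − π) = control pass rate.
- T2 (0.74): ρ = 0 gives π = 0.860, ozone mean 4.30, difference 0.60. ρ = 0.5 gives 0.815, 4.08, 0.38. ρ = 1 gives 3.70, 0. To reach 4.24 (π = 0.848), ρ must be (0.74 − 0.848²)/(0.848 × 0.152) ≈ 0.16. A larger ρ gives less than 0.54.
- T1 (2.49/8 = 0.311): ρ = 0 gives an ozone mean of 4.46, ρ = 0.5 gives 3.47 and ρ = 1 gives 2.49. The printed value is 2.00, below the whole range.

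So the literal reading reaches the T2 figure only with complete separation of the arms and low correlation, and no ρ from 0 to 1 gives the printed T1 row.

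**The case against.** A reader might infer from the singular and plural wording that ozone patients had a smaller operation and that the T2 result reflects this. The documents do not support that. The eligibility rule covers one or more teeth in both arms. The Group C text is a loose paraphrase of the Group T text, even using another group label, and nothing records a different extent of surgery. Step 4 shows that the explanation also misses the T1 row.

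The strongest objection to the rest is that allocation is described as random. Chance imbalance in a prognostic factor is then already covered by the error rate of the unadjusted test, and the rank-sum P is at most 0.00015. This stands: the omission does not invalidate the test, and adjustment is not the repair of a bias. What remains is that the estimate can be shifted in this sample by a factor nobody can see. Imbalances of the assumed size do occur here: the non-oncologic (ost) patients in Table 2 are 31.6% against 53.2%, a gap of 21.6 points. That is one row of several, so it is illustrative only.

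It is also fair that dental history was recorded and that unnamed clinical covariates might include extent of surgery. So the variables may exist and may have been screened. They are still not named, not shown by arm and not certain to enter any model. Finally, if a single index socket was scored in each patient, the mechanism in step 3 largely disappears; the documents do not say which was done.

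**Conclusion.** The point holds as a weakness in reporting and analysis. Extent of surgery and reason for extraction vary by design, are invisible by arm, and are handled at best by a significance screen in a dichotomised model. No adjusted analysis of the T2 score, or of any other phase score, is specified.

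Under the assumptions in steps 2 and 3, a 95% chance imbalance is worth 0.15 T2 points with independent sites, roughly a quarter of 0.54, falling to 0.08 at correlation 0.5 and to 0 at correlation 1. With a directly assumed loss of 0.5 to 1.5 points per multi-tooth case, the range is 0.10 to 0.29. The true figure cannot be computed because the documents give no extraction counts. The shift could go in either direction, and none of these values accounts for the whole T2 difference.

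The difference in surgical wording needs reconciling for its own sake. It carries no weight as evidence about what was done.

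**What to change.** 1. Make the Group T and Group C surgical descriptions in section 2.3 consistent apart from ozone, or state that they differ and how.
2. From existing charts, take the number of teeth planned for extraction, using pre-treatment radiographs and records, and the reason (caries, periodontitis or both). Use the planned number: the documents do not show that the number actually removed was settled before allocation. Add both variables to Table 2 by arm.
3. Estimate the arm difference in each IPR phase score and in the total, with a confidence interval, from a model with arm, number of teeth (1 versus 2 or more) and reason as fixed covariates, whatever their univariable P-values. At T3 the ozone arm has SD 0, so adjustment will add little there.
4. Repeat the T2 comparison in single-extraction patients if both arms have enough of them. If the tabulation in step 2 shows that tooth count nearly coincides with arm, neither this subset nor the model can separate the two, and the report should say so.

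The cost is chart review for 117 patients, a few lines of SAP text, and two or three degrees of freedom (one for number of teeth, one or two for reason). No new visits or procedures are needed. The single-extraction analysis will be smaller and less precise, and should be labelled as a sensitivity analysis.

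### Do the extra ozone sessions in 9 of 38 patients, and the differing wording on delivery, call for a different 14-day analysis?

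*Combined protocol and SAP*

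**What the plan says.** The GROUP T part of section 2.3 describes ozone at surgery by injection around the socket together with "insufflation of the same mixture in the post-extraction site for at least 1 minute". It then states that "each patient was scheduled for supplementary visits during which the OxigenOzone mixture was applied at T1" and also at T2 and T3. The next sentence reports that "in 9 patients the mixture was applied twice a week within T2, until complete clinical healing or in case of ONJ sequestration formation", on the condition "When possible, depending on the patient's compliance and willingness". No such sessions are described for controls.

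Delivery is worded differently elsewhere. The allocation paragraph at the start of the document says the 38 patients were selected "to receive ozone therapy by insufflation to the post-extraction site". Table 3 lists as adjuvant therapy only "Injections of a 15 mL mixture of Oxygen-Ozone". The aim speaks of infiltration. The route used at T1 to T3 is not given.

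Section 2.4 compares the two groups by the chi-square or Fisher test for categorical variables and by Student's t or the Wilcoxon-Mann-Whitney test for continuous ones. The results table there pools all 38 ozone patients against 79 controls at each time point and does not separate patients by schedule.

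**The concern.** Almost a quarter of the ozone group had a more intensive exposure. They were chosen for it after allocation, partly by their own willingness, and its duration was tied to healing, which is what the IPR scale measures. If the phrase about T2 means the first 14 days, the extra sessions came before the T2 score. T2 is the only row with a significant difference in favour of ozone (P <0.001). T1 is significant in favour of control. T3 (3.00 against 2.96) and the total (9.37 against 9.15) are slightly higher with ozone but not significant.

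A reader who takes the T2 row as the effect of the T0-T3 schedule alone would be crediting that schedule with whatever the extra sessions contributed. With delivery worded in several ways, the reader might also be unsure which treatment was tested.

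**Working it through.** **Inputs.** From the results table in section 2.4: T2 mean (SD) 4.24 (1.51), median [Q1, Q3] 5 [4, 5], n = 38 for ozone; 3.70 (1.02), 4 [3, 4], n = 79 for control. From Table 4 (the IPR scale): T2 has five items scored 0 or 1, so scores are integers from 0 to 5. From section 2.3: 9 patients with extra sessions, 9/38 = 23.7%.

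**Reproducing the stated result.** The only integer totals that fit the means are 161 (161/38 = 4.24) and 292 (292/79 = 3.70), a difference of 0.54. Four score distributions fit the ozone row; 102 were found for the control row in a search that capped the counts of extreme scores. Over sampled pairs of these, the two-sided rank-sum P runs from 0.000003 to 0.00015, in line with the printed P <0.001. From the means and SDs, Student's t gives P = 0.024 and Welch's t gives P = 0.051.

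**Contrast for the other 29 patients.**
- Lowest: the 9 all scored 5. (161 − 45)/29 = 4.00, and 4.00 − 3.70 = 0.30.
- Highest: the 9 were the lowest scorers, whose sum is 18 or 19 in the four distributions. (161 − 19)/29 = 4.90 and (161 − 18)/29 = 4.93, so the difference is 1.20 to 1.23.

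**Largest share from the 9.** 9 × (5 − 3.70)/38 = 0.308, and 0.308/0.54 = 57%. This is a ceiling effect: 26 or 27 of the 38 ozone patients score 5 in the fitting distributions, and any nine of them would give the same 57%. With nine removed, 17 or 18 of the remaining 29 still score 5, against a control median of 4.

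**Tests at the low end.** On the reconstructed scores the rank-sum P is 0.0009 to 0.012. The 29 scores then have mean 4.00 and SD 1.67. For Student's t the pooled variance is (28 × 1.67² + 78 × 1.02²)/106 = 1.50, the standard error is √[1.50 × (1/29 + 1/79)] = 0.266, t = 0.30/0.266 = 1.1, and P is about 0.26; Welch's t gives 0.36. The t-based results are therefore weaker, but Welch already gives 0.051 on all 38. The table's footnote names a Wilcoxon test.

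**Had all 38 followed the common schedule.** The 9 scores under that schedule are unknown and could lie anywhere from 0 to 5. Lowest: (116 + 0)/38 − 3.70 = −0.65. Highest: (143 + 45)/38 − 3.70 = +1.25. The narrower 0.30 to 1.23 describes who is left after self-selected patients are dropped, so it cannot be read as the effect of the common schedule.

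**The case for a change.** The strongest case for a change is that it costs little. One extra table from existing data would show the 29 and the 9 separately, labelled descriptive, and one sentence would say that the pooled result includes optional extra sessions. The facts behind this case stand: the 9 are a real departure from a single schedule, their selection and duration depended on events after allocation, and the published row cannot separate the two exposures.

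It does not carry the point further for four reasons. First, the text schedules T1 to T3 for each patient and then reports more frequent application in 9; nothing says those visits were dropped, so the extra sessions read as additions, not as a replacement schedule. Second, the 29 and the 9 differ in willingness and perhaps in healing, so neither subgroup mean estimates the effect of a schedule, and a group of 9 is imprecise. Third, the proposal keeps all 38 as assigned as the main analysis, which the table already shows. Fourth, the document has no conclusion section that credits the result to the T0-T3 schedule, and section 2.3 discloses the extra sessions openly.

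On delivery, the allocation paragraph, Table 3 and the GROUP T text differ and must be reconciled by the sponsor. It is not for this review to say which is right. The difference enters none of the figures above and does not alter who is compared with whom.

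**Conclusion.** No change to the analysis follows. The pooled T2 difference of 0.54 compares everyone as assigned and estimates ozone with optional extra sessions, which fits the stated aim of comparing extraction protocols with and without ozone. A reader can understand it that way from section 2.3. The contrast for the 29 patients could be anywhere from 0.30 to 1.23 points. It stays positive throughout, and the rank-sum P is at most 0.012 at the low end, although a t test there would not reach 0.05.

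This rests on the T2 row being printed correctly and on integer scores from 0 to 5. One caution applies: the ozone subscale means sum to 2.00 + 4.24 + 3.00 = 9.24 (351 points), but the printed total is 9.37 (356 points). If the 5 missing points all belonged to T2, which is an assumption, the ozone mean would be 166/38 = 4.37 and the low end would rise to (166 − 45)/29 − 3.70 = 0.47.

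What remains is a minor reporting clarification: the passages on schedule and delivery need to agree.

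### Local signs are compared only as summed IPR scores, so the documents cannot show which signs occurred, in how many patients, or whether they were more frequent with ozone

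*Combined protocol and SAP*

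**What the plan says.** Section 2.3 (Healing Evaluation and follow-up) describes the IPR items as "each ranging from 0 to 1, resulting in a total score ranging from 0 to 16". In the IPR scale table, score 1 is the favourable state for every item.

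- **Day 3–5 (T1, 8 items):** bleeding, granulation tissue, haematoma, tissue colour, incision margins (the unfavourable state includes partial or complete necrosis), then "Suppuration Edema NRS (1–10) Pain NRS (1–10", where oedema and pain score 0 at NRS 6–10.
- **Day 14 (T2, 5 items):** re-epithelialisation, tissue colour, scar, suppuration, pain.
- **Week 6 (T3, 3 items):** scar, tissue colour, pain.

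The items are then added: "At the end of the follow-up period, the total IPR score was computed, with scores spanning from 0 to 16". The results table in section 2.4 (also numbered Table 4) compares the three phase sums and the total, and nothing else, between 38 ozone and 79 control patients. Section 2.4 has general sentences on counts and on Chi-square or Fisher tests for categorical variables, but applies them to no IPR item. Pain intensity was recorded at each visit, yet no pain result by arm is given. There is no adverse-event definition and no harms analysis.

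**The concern.** The test arm has gas injected around the socket and insufflated into it, with further applications at later visits, so local tolerability is a basic question. The signs that bear on it were recorded one by one, but a sum does not say which sign was present or how many patients did badly.

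The two early phases also point in opposite directions. Ozone is lower at T1 (2.00 vs 2.49, P 0.006) and higher at T2 (4.24 vs 3.70, P <0.001), and the differences largely cancel in the total (9.37 vs 9.15, P 0.275). Nothing printed says which items drive either difference.

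The T1 level is itself surprising: a mean near 2 of 8 means that about six of eight items were unfavourable in a typical patient of either arm. Either such signs were common and went unreported, or the coding is wrong and the T1 and total rows need correcting.

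**Working it through.** **Inputs** (results table, section 2.4; item direction from the IPR scale table)

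| Row | Ozone, N=38: mean (SD), median [Q1, Q3] | Control, N=79: mean (SD), median [Q1, Q3] |
|---|---|---|
| T1, of 8 | 2.00 (0.870), 2 [1, 2.75] | 2.49 (0.875), 2 [2, 3] |
| T2, of 5 | 4.24 (1.51), 5 [4, 5] | 3.70 (1.02), 4 [3, 4] |
| T3, of 3 | 3.00 (0), 3 [3, 3] | 2.96 (0.192), 3 [3, 3] |
| Total, of 16 | 9.37 (1.79), 9.5 [9, 10] | 9.15 (1.38), 9 [8, 10] |

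**Method.** Scores are whole numbers, so one can list every set of counts that reproduces the printed N, mean, SD and quartiles after rounding (R default quantiles).

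**1. Reproducing the printed P-values** (two-sided Wilcoxon rank-sum, normal approximation).
- T3: 3 of 79 controls at score 2 gives P = 0.2297; printed 0.230.
- T1: P runs from 0.0016 to 0.0063 over the feasible sets, which includes the printed 0.006.
- T2: P is at most 0.00016; printed <0.001.

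**2. Day 3–5, ozone.** Exactly one set fits: 12 patients at 1, 16 at 2, 8 at 3, 2 at 4.
- Mean: (12×1 + 16×2 + 8×3 + 2×4)/38 = 76/38 = 2.00.
- SD: √[(180 − 76²/38)/37] = √(28/37) = 0.870.
- Patients scoring 2 or less: 12 + 16 = 28 of 38 (74%).

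**3. From scores to signs.** A T1 score of 2 or less means at least 8 − 2 = 6 unfavourable items. Only five items lie outside suppuration, oedema 6–10 and pain 6–10, so each such patient had at least one of these three. A score of 1 means 7 unfavourable items, hence at least two of the three. This gives at least 28/38 with one or more, and at least 12/38 (32%) with two or more.

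**4. Day 3–5, controls.** 292 sets fit. Between 40 and 58 of 79 (51–73%) score 2 or less; requiring the printed P of 0.006 narrows this to 44–58. At most 10 of 79 (13%) score 1 or less.
- Fisher P for 28/38 against 40/79 is 0.027, against 44/79 it is 0.07, and against 58/79 it is 1.0.
- Fisher P for 12/38 against 10/79, the smallest possible gap, is 0.022.

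**5. Day 14.** Four sets fit the ozone row. Counts at scores 0 to 5 are (3,1,1,0,7,26), (3,1,0,3,4,27), (3,0,3,0,5,27) and (2,3,0,1,5,27). So 2–3 of 38 (5–8%) score 0, meaning all five items unfavourable, and 3–5 of 38 (8–13%) score 1 or less. In controls 102 sets fit, with 0–3 of 79 (0–4%) at 0 and 0–7 of 79 (0–9%) at 1 or less.
- Fisher P for zeros runs from 0.03 (3 vs 0) to 0.66 (2 vs 3).
- For scores of 1 or less, 3/38 against 7/79 gives P = 1.0.

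The 2–3 zeros depend on the quartiles; the ozone mean and SD alone allow 0–3.

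**6. Do the rows add up?**
- Control: 2.49 + 3.70 + 2.96 = 9.15, as printed.
- Ozone: 2.00 + 4.24 + 3.00 = 9.24, but 9.37 is printed. In points, 76 + 161 + 114 = 351 against 356, a gap of 5.

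**7. If T1 had been entered in reverse.** Ozone: (8 − 2.00) + 4.24 + 3.00 = 13.24. Control: (8 − 2.49) + 3.70 + 2.96 = 12.17. The like-for-like sums as printed are 9.24 and 9.15. T1 would then favour ozone (6.00 vs 5.51), and both mean totals would move from the 5–10 band (acceptable healing) to the 11–16 band (excellent).

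**The case against.** **The counts do not attribute anything to ozone.** A reader might infer local harm from 28/38 alone. The same counting gives at least 40/79 controls, and both figures are lower bounds because a patient scoring above 2 may also have such a sign. Day-14 zeros overlap too (2–3/38 vs 0–3/79). The ozone arm also had more high-risk patients (57.9% vs 44.3%, Table 2). This stands. The wider gap at T1 scores of 1 or less compares scores, not named signs, and restates the T1 deficit already printed.

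**Nothing is concealed at phase level.** A reader might infer that an early disadvantage was hidden. The lower ozone T1 score and its P-value are in the first row of the results table. This stands too; what is missing is the item detail behind it.

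**The reconstruction is conditional.** The ozone rows do not add up, so at least one is wrong. The gap of 5 points equals, for example, one T2 zero entered as 5, which would leave 1–2 zeros, although the printed total SD and quartiles fit the printed T2 row better. Reversed T1 coding, or missed T2 visits stored as 0, would remove much of the apparent signal. This stands as a limit on certainty, and is itself a reason for a source check.

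**The scale is meant to be summed, and the general test wording could cover its items.** Summing is legitimate for a healing endpoint, and an item table changes no planned test. But the general wording names no IPR item and no item result is shown, so the gap remains.

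**Conclusion.** The point holds as a gap in analysis and reporting, together with an unresolved question about the data. From the documents one cannot say which local signs occurred, in how many patients, or whether they were more frequent with ozone.

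The size in step 3 to step 5 of the working rests on three assumptions: 1 is favourable for every item, the printed phase rows are correct, and scores are complete in all 38 and 79 patients. On those assumptions, suppuration, oedema 6–10 or pain 6–10 was present at day 3–5 in at least about three quarters of ozone patients and at least half of controls, and a few ozone patients failed every day-14 item inside a row that favours ozone.

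The documents do not support the further inference that ozone caused these signs, nor that the day-14 difference is spurious. The mismatch in the ozone total (9.24 vs 9.37) needs no such assumption: the printed ozone rows cannot all be right for the same 38 patients.

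**What to change.** 1. Before reporting, check against the visit sheets the direction in which T1 items were coded, every T2 score of 0 (true failure or missed visit), and the ozone total. Correct the affected rows and P-values.
2. Add a descriptive by-arm table of the recorded T1 and T2 items with n/N, risk difference and exact 95% CI. Include bleeding, haematoma, suppuration, oedema 6–10, pain 6–10, margin necrosis or incomplete closure (as recorded) and partial re-epithelialisation.
3. Add the by-arm count of patients with a T2 score of 1 or less.
4. State the T2 difference together with these counts and the worse T1 score, as they stand after the check.

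Cost: one table from data already recorded and a source check, which for the T2 zeros and the ozone total is confined to a small set of records. The downside is more secondary comparisons in small groups, so the table should be labelled descriptive and carry no claim of significance. No planned test changes unless the check alters the data.
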